#### 7.1 Extent of Exposure

The following information will be summarized using descriptive statistics by cohort and treatment group as well as overall:

- Overall duration of exposure (days), calculated as (Date of explantation of last unit of any type Date of implantation of first unit +1)
- Number of VC-02-300 units implanted
- Duration of exposure (days) of VC-02-300 units, calculated as (Date of the last VC-02-300 explantation Date of first VC-02-300 unit implantation + 1)
- Number of VC-02-20 units implanted
- Duration of exposure (days) of VC-02-20 units, calculated as (Date of the last VC-02-20 explantation Date of first VC-02-20 unit implantation + 1)
- The number of subjects with total planned number of units implanted. If total planned number of units not implanted, then summarize the reason all units not implanted
- Investigator's overall assessment of the implant surgical procedure
- The number and percentage of subjects with a premature explanation of a VC-02-300 unit
- The number and percentage of subjects with a premature explanation of a VC-02-300 unit who remained in the study
- Reason for premature explanation of a VC-02-300 unit

A listing of implantation and explantation information as well as a separate listing containing investigational product incision information will also be provided.

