## 8.1.4. Adverse Events of Special Interest (AESI)

Certain AEs may require additional investigation to ensure appropriate information and data are captured to appropriately evaluate the clinical development of VC-02. These are considered adverse events of special interest (AESI) and may include but are not limited to:

- AEs leading to the unexpected or premature explantation of VC-02-300 or sentinel units are considered AESI.
- AEs that result in early withdrawal from the study.

• Severe hypoglycemic events occurring after VC-02 implantation possibly or definitely related to VC-02.

If an AESI occurs, the Sponsor may request that additional data be collected for these events.

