## 10.4.3. Primary Safety Analysis

Unless otherwise specified, the SAS (for both Cohort 1 and Cohort 2 subjects who meet the SAS criteria) will be used for the primary safety summarizations. Adverse events and SAEs will be summarized by SOC, by severity, and by relationship. This will be done by treatment group and overall. The summarization of AEs will focus on only those events that are TEAEs, but the AE listings will include all reported AEs regardless of when they started.

Other safety data, such as vital signs and clinical laboratory data will be summarized by study visit and treatment group. Where appropriate, change from baseline in safety data will also be summarized in a similar manner.

The number of subjects undergoing a premature VC-02-300 unit explant will be provided in a listing which includes the reason for explantation (i.e., safety issue, malfunction, damaged, planned explant, etc.)

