8.0 (Amendment #9) 18 May 2020	3.1	Changed the number of implants per subject in VC02-101 to "twelve (12) units. Of the twelve implanted units, no more than four ten (104) will be VC-02-300 units, and the remainder will be VC-02-20 units. For example, if ten (10) VC-02-300 units are implanted, up to two (2) sentinels may also be implanted."	The number of implants was changed in VC02-101 Protocol Version 8.0 (Amendment #9).
		Removed language about implants in VC02-102 subjects.	Only three subjects were enrolled in the VC02-102 study.
8.0 (Amendment #9) 18 May 2020	3.2.1	Changed the number of subjects enrolled in Cohort 2 from "40" to "60", and the total number of subjects enrolled to "75".	The number of implants was changed in VC02-101 Protocol Version 8.0 (Amendment #9).
8.0 (Amendment #9)	3.2.3	Updated description of the number of implants in VC02-101 Cohort 1 and Cohort 2 subjects,	The number of implants was changed in VC02-101 Protocol Version 8.0 (Amendment #9).

Protocol Version # Date	SAP Section	Modification	Description and Rationale
18 May 2020		the duration of the study, and the number of subjects enrolled in Cohort 2 as well as overall.	
8.0 (Amendment #9) 18 May 2020	4.2	Updated the definition of the FAS to exclude subjects enrolled in VC02-101 Cohort 1 or VC02- 102 Cohort 1.	The FAS was updated in VC02-101 Protocol Version 8.0 (Amendment #9).
8.0 (Amendment #9) 18 May 2020	4.3	Updated the SAP Windows for the visits Week 104 and Week 105 (Follow-Up Visit).	The Week 104 visit did not need an upper range since it is the last visit of the study. The Week 105 (Follow-Up Visit) did not need SAP Windows.
8.0 (Amendment #9) 18 May 2020	4.4	Added analysis rules for dropouts and missing data for MMTTs and rules for determining TEAEs using missing or partial dates.	Clarified based on safety deliverables.
8.0 (Amendment #9) 18 May 2020	4.6.1	Updated derivations and visits for the analysis of the 2-hour MMTTs	The 2-hour MMTT visits were changed in VC02-101 Protocol Version 8.0 (Amendment #9).
8.0 (Amendment #9) 18 May 2020	4.6.2	Removed language pertaining to subjects who do not complete the 2-hour MMTT.	The C-peptide must be measurable to perform the analysis.
8.0 (Amendment #9) 18 May 2020	4.6.3	Updated the derivation for baseline average weekly frequencies of subject-reported HEs. Added statement "Data should	Clarified based interim safety summaries. The number of implants was changed in VC02-101 Protocol

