#### VC02-102:

The comprehensive safety profile of VC-02 combination product implanted for up to four months as measured by:

- All reported AEs
- The incidence of subjects requiring a premature explant due to safety, tolerability, or malfunction issues.

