#### **323 Dosing Schedule**

#### VC02-101 and VC02-102 Cohort 1:

At a minimum, the first three (3) subjects in Cohort 1 will be enrolled sequentially in order to assess safety and tolerability data thru Week 2 before implanting the next subject. For example, data thru Week 2 from the first subject will be formally reviewed by the Sponsor prior to allowing the Investigator to implant the next subject. If a treatment-related serious adverse event (SAE) is observed within the first two weeks in the subject, the implantation of the next subject will be postponed until consultation between the Sponsor and Investigator has devised appropriate safeguards. Overall, if no treatment-related SAEs are observed with the first three (3) subjects after each has reached Week 4, additional Cohort 1 enrollment may then be performed in parallel.

[figure not shown]
Initially, up to six sentinels will be implanted in the first three (3) Cohort 1 subjects in order to provide sufficient histologic data to assess preliminary safety and tolerability. The first three (3) subjects enrolled in Cohort 1 will not be implanted with VC-02-300 units. After the first three subjects are enrolled in Cohort 1 and initial safety and tolerability is confirmed, VC-02-300 units may then be implanted in subsequent, enrolled subjects and the stimulated C-peptide levels will be monitored. These additional Cohort 1 subjects may be implanted with up to two (2) VC-02-300 units and up to six (6) VC-02 sentinels total. The decision as to the number of VC-02-300 units implanted in subsequent subjects will be data-driven and this number may be reduced. However, if no VC-02-300 units are implanted in these additional; Cohort 1 subjects, up to ten (10) VC-02 sentinels may instead be implanted. No subjects enrolled in VC02-102 will receive VC-02 300 units and will have up to six smaller, VC-02-20 (sentinel) units implanted in anatomical locations involving the trunk or extremities (e.g., back, flanks, arms, legs, and abdomen) suitable for implantation, as deemed appropriate by the Investigator and/or Surgeon after consultation with the Sponsor. Documentation of the implant plan for a subject will be provided to the Investigator by the Sponsor. Implantation will be executed under an anesthetic with or without sedation.

The total duration of treatment (implantation) may be up to two (2) years for each VC02-101

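### The only planned premature-explant count covers VC-02-300 units, so it does not match the secondary safety endpoint and cannot register an event in any sentinel-only subject

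*SAP*

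**What the plan says.** **Endpoint.** SAP 2.2.2 lists, separately for VC02-102, "The incidence of subjects requiring a premature explant due to safety, tolerability, or malfunction issues". It uses the same wording for VC02-101, as does Protocol 2.2.2. The definition is per subject, is limited to three reasons, and names no unit type.

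**Planned output.** SAP 7.1 (Extent of Exposure) gives three items on premature explant, by cohort and treatment group and overall. The first is "The number and percentage of subjects with a premature explanation of a VC-02-300 unit", where the fifth-last word or so is evidently a slip for explantation. The other two are how many of those subjects stayed in the study, and the reason. All three are limited to VC-02-300 units. Protocol 10.4.3 has the same limit: "The number of subjects undergoing a premature VC-02-300 unit explant will be provided in a listing".

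**Who has no VC-02-300 unit.** SAP 3.2.3 states "No subjects enrolled in VC02-102 will receive VC-02 300 units and will have up to six smaller, VC-02-20 (sentinel) units". The first three Cohort 1 subjects also receive none (Protocol 3.1; SAP 3.2.3). Later Cohort 1 subjects may be sentinel-only (SAP 3.1), and Protocol 7.8.1 allows up to twelve sentinels in a Cohort 2 subject. SAP 4 puts all such subjects in a treatment group of their own, with zero VC-02-300 units.

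**Sentinels elsewhere.** Protocol 8.1.4 includes among the adverse events of special interest (AESIs) "AEs leading to the unexpected or premature explantation of VC-02-300 or sentinel units". SAP 7.2.4 repeats this.

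**The concern.** A named secondary safety endpoint covers all implanted units, but the stated counting rule covers one unit type. For subjects without that unit type the count is zero by rule, and in a table it looks like an observed zero. For VC02-102 this is one of only two secondary safety measures in SAP 2.2.2. For VC02-101 Cohort 1, safety and tolerability are the main purpose. Early loss of a sentinel is an event that the documents themselves recognise, yet no planned table gives its incidence.

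**Working it through.** The endpoint is descriptive. The documents give no sample size, power or expected rate for it, so there is no planned figure to reproduce. The check applies the SAP 7.1 counting rule and the SAP 2.2.2 definition to the same subjects.

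**Step 1: the two rules.**
- SAP 2.2.2: a subject counts if any unit is explanted prematurely for safety, tolerability or malfunction.
- SAP 7.1: a subject counts if at least one VC-02-300 unit is explanted prematurely. Reasons are tabulated, but the count is not restricted to the three. Protocol 10.4.3 names a planned explant among the example reasons.

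**Step 2: VC02-102.** The SAP revision table records: "Only three subjects were enrolled in the VC02-102 study". Each has 0 VC-02-300 units.

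| Subjects with premature sentinel explant | SAP 2.2.2 incidence | SAP 7.1 count |
|---|---|---|
| 0 | 0/3 = 0% | 0/3 = 0% |
| 1 | 1/3 = 33.3% | 0/3 = 0% |
| 2 | 2/3 = 66.7% | 0/3 = 0% |
| 3 | 3/3 = 100% | 0/3 = 0% |

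The same holds for the whole treatment group with zero VC-02-300 units. SAP 7.1 also does not split by protocol: VC02-102 is folded into Cohort 1, so its own endpoint has no row.

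**Step 3: subjects with both unit types.** If only a sentinel is explanted early, SAP 2.2.2 counts the subject and SAP 7.1 does not.

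**Step 4: how many sentinel-only subjects.** SAP 3.2.3 describes the first three Cohort 1 subjects under a heading that joins VC02-101 and VC02-102. Protocol 3.1, which is VC02-101 alone, says that its own first three get no VC-02-300 units.
- If the two groups of three are the same subjects: at least 3.
- If they are separate, as Protocol 3.1 suggests: at least 3 + 3 = 6.

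**Step 5: share of the safety set.** The enrolment cap is 15 + 60 = 75. If VC02-102 is additional to it, the total is 75 + 3 = 78.
- 3/75 = 4.0%
- 6/78 = 7.7%
- 6/75 = 8.0%

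The range is therefore about 4% to 8%, before any later sentinel-only subjects.

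**Step 6: illustration with assumed rates.** The documents give no rate, so take a per-subject probability p of premature sentinel explant of 5%, 10% or 20%. The chance that at least one real event occurs among n sentinel-only subjects and is tabulated as zero is 1 − (1 − p)^n.
- n = 3: 14%, 27%, 49%
- n = 6: 26%, 47%, 74%

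**Step 7: other outputs.** SAP 7.6 has no premature-explant summary, and the tables in SAP 7.2.7 include none for AESIs. SAP 7.1 plans a general implantation and explantation listing, with no count and no stated flag for premature explant.

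**The case against.** **The events are not lost.** Early sentinel removal can appear in the explantation listing and, where an adverse event caused it, in the AE records. A subject who withdraws has all units explanted, and so appears in disposition with a reason (SAP 5.1) and, if an AE was the cause, in the tables of TEAEs leading to withdrawal. This stands. For three VC02-102 subjects a listing goes a long way. None of these outputs is the endpoint's incidence, however, and a subject who loses one sentinel and stays in the study reaches no planned count.

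**The SAP 7.1 rows are exposure data, not the endpoint analysis.** SAP 7.1 does not say that they analyse the SAP 2.2.2 endpoint. If they do not, the endpoint has no planned tabulation at all, and the remedy is the same.

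**The label warns the reader.** A count of VC-02-300 explants in a group defined by having none is visibly not applicable, and nothing in the SAP forbids showing it so. This is fair, but the SAP does not call for it, and the overall column carries no such warning.

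**Premature has no reference point for sentinels.** Their explant times are set by the Sponsor (Protocol 7.8.1). This stands as a gap that the fix must close. Protocol 5.1.4 provides for a documented explant plan for each subject, which can serve as the reference.

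**Stronger readings that the documents do not support.** A reader might infer that the endpoint itself is zero by construction. It is not: the definition is neutral as to unit type, and only the tabulation is fixed. A reader might also infer a biased dose comparison, with a rise from a baseline that cannot move. No such comparison of this outcome is planned; SAP 4 says displays are primarily descriptive, with no hypotheses about treatment effects.

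**Conclusion.** The endpoint and its only planned tabulation do not match. As written, VC02-102 contributes 0/3 and the group with zero VC-02-300 units shows 0% whatever happens. Early sentinel loss in subjects with both unit types is uncounted.

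At least 3 subjects are affected, or 6 on the reading that Protocol 3.1 favours, which is about 4% to 8% of a full safety set. This assumes that implant surgery was attempted in all three VC02-102 subjects, so that they are in the safety set, and that both VC02-101 cohorts fill. Further sentinel-only subjects would raise the share; their number is not given.

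A firm minimum of 6, or a third of Cohort 1 (6/18), might be inferred. The documents do not settle either figure: the SAP's joint Cohort 1 heading leaves open whether the two groups of three are distinct, and whether VC02-102 counts within the cap of 15. The mismatch itself depends on neither.

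This should be corrected, because the stated rule gives a wrong incidence for a named safety endpoint. It does not affect the primary efficacy analysis.

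**What to change.** In SAP 7.1, add as the stated analysis of the SAP 2.2.2 endpoint:
- the count and percentage of subjects in whom any VC-02 unit, VC-02-300 or sentinel, was explanted prematurely for safety, tolerability or malfunction, by protocol, cohort and treatment group;
- a definition of premature for analysis only: earlier than the subject's Sponsor-documented explant plan, and for one of those three reasons. Planned sentinel explants then drop out.

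Keep the VC-02-300 rows as a sub-breakdown, and show them as not applicable for subjects who received no VC-02-300 unit. Extend the listing in Protocol 10.4.3 to both unit types. The VC02-102 protocol is not among the documents, so its wording should be checked for the same limit.

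The cost is one extra set of table rows and matching protocol wording. The explantation listing is already planned, but its data must record the planned explant date and the reason for each unit. The reported premature-explant rate may rise. No sample size, design or clinical decision changes.

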## 7.2 Adverse Events

All AEs with a start date occurring between Visit 2 (Week -3) and through the subject's last visit must be recorded. At the conclusion of the trial, any ongoing AEs will be followed until at least 28 days after the final explanation procedure to determine the final reported outcome of the event.

For SAEs, including pregnancy reports, the active reporting period to the Sponsor begins from the time the subject provides informed consent through and including 28 days after the final explantation of all of the investigational product units.

The reporting period for AEs and SAEs may overlap with the timing of the subject's participation in the mandatory, 1-year follow-up study. Further details on how to report ongoing AEs spanning the period between the VC02-101 or VC02-102 protocols and follow-up study will be outlined in the separate follow-up protocol.

For this study, missing or partial AE start and/or stop dates will not be imputed using statistical programming. However, rules for determining if an AE is treatment-emergent or non-treatment-

emergent will be used for partial dates; these rules are discussed in Section 4.4 of this SAP.

#### 72.1 Treatment-emergent Adverse Events

A treatment-emergent adverse event (TEAE) is defined as an AE that starts on or after the date of implant surgery.

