## 5.2. Immunosuppression Medications

An immunosuppressive regimen will be prescribed for each subject to facilitate the engraftment and long-term function of implanted VC-02 units. The overall regimen may include the following agents (\**Day 1 is Implant Day*):

- Induction (Cohort 1)
  - Basiliximab: Recommended course of 20 mg IV on Day 1 and Day 5. However, it may be administered as early as Visit 2 (Week -4).
- Induction (Cohort 2)

If data collected from Cohort 1 indicate sufficient engraftment and cell viability is achieved with basiliximab, its use will continue in Cohort 2. However, if data from Cohort 1 and/or data collected in subsequent subjects in Cohort 2 indicate insufficient cell viability is achieved, the following agent may be utilized:

- Anti-thymocyte globulin (ATG) recommended course:
  - Day -2 (0.5 mg/kg IV) required dose
  - Day -1 (1.0 mg/kg IV) required dose
  - Day 1 (1.5 mg/kg IV) required dose
  - Up to two additional 1.5 mg/kg/day IV doses of ATG may be administered (on Day 2, and/or Day 3). Prior to any additional dose administration of ATG, an absolute lymphocyte count (ALC) will be obtained locally. If the ALC has been reduced by at least 90% versus the pre-ATG administration level, additional dose(s) of ATG may not be required. The Investigator should contact the Sponsor to determine the need for additional dosing.

However, ATG may be administered using the above dosing schedule as early as Visit 2 (Week -4).

• Maintenance (both Cohorts)

The starting doses and target serum trough concentration levels listed below are recommendations. As determined by the Investigator and after consultation with the Sponsor, the doses and target trough levels may be adjusted.

- Mycophenolate mofetil (MMF): Recommended starting dose of 1 gm PO BID as early as Visit 2 (Week -4). Adjust the dose downward for gastrointestinal side effects. Mycophenolic acid (Myfortic) may be taken alternatively to alleviate such side effects. Trough level measurements for MMF are not required.
- Tacrolimus:

- If combined with MMF: Recommended starting dose of 2 mg PO BID as early as Visit 2 (Week -4); target serum trough concentration level of 10-12 ng/mL during the first three (3) months. Adjust the dose to maintain a serum trough concentration level of 7-9 ng/mL thereafter. Serum creatinine values should also be collected in conjunction with Tacrolimus trough levels in order to monitor for potential renal toxicity.

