### 8.1.5. Period of Observation and Reporting

All AEs with a start date occurring between Visit 2 (Week -4) and through the last subject visit must be recorded on the CRF. During the study, sites should query subjects on the status of any ongoing AEs at subsequent clinic visits. Depending on the reported event, the Investigator may need to follow-up on the status of AEs with the study subject between visits (e.g., phone, text, or email). At the conclusion of the trial, any ongoing AEs will be followed until at least 28 days after the final explantation procedure to determine the final reported outcome of the event.

For SAEs, including pregnancy reports, the active reporting period to the Sponsor begins from the time the subject provides informed consent through and including 28 days after the final explantation of all of the investigational product units.

SAEs occurring after the period of observation has ended should be reported to the Sponsor if the Investigator becomes aware of an event. At a minimum, all SAEs the Investigator assesses as possibly related to the investigational product are to be reported to the Sponsor.

The reporting period for AEs and SAEs may overlap with the timing of the subject's participation in the mandatory, long-term follow-up study. Further details on how to report ongoing AEs spanning the period between the VC02-101 protocol and follow-up study will be outlined in the separate follow-up protocol.

All AE reporting, including SAEs and SUSARs, will be carried out in accordance with applicable regulations.

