#### 2.2 Endpoints

#### 2.2.1 Primary Endpoint

#### VC02-101 and VC02-102 Primary Endpoint / Cohort 1:

- Targeted safety and tolerability profile, inclusive of:
  - The incidence of adverse events (AEs) with causality related to VC-02 combination product, the surgical procedures required for VC-02 administration, and the immunosuppressive drug regimen.
  - The incidence of off-target growth as evidenced by implanted VC-02 units via lumen ultrasound measurements, or by histological examination of explants.
  - The incidence of confirmed immune sensitization defined by presence of donor anti-human leukocyte antigen (HLA) antibodies absent prior to implant in conjunction with either confirmatory histological observations from at least one explanted unit and/or the presence of clinical symptoms.
  - Implant tolerability assessments (e.g., fever, erythema, pain, tenderness, induration) for up to four hours post-implantation and at subsequent visits.

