#### 4.2 Analysis Sets

The Full Analysis Set (FAS) is the intent-to-treat (ITT) set of subjects. This set is defined as all subjects who were enrolled into VC02-101 and received implantation of at least one VC-02-300 or sentinel unit on Study Day 1. Note that Cohort 1 in VC02-101 and in VC02-102 have no efficacy endpoints, so the subjects from Cohort 1 in VC02-101 and VC02-102 are not included in the FAS. All Cohort 2 VC02-101 efficacy summaries/analyses will be performed on the FAS. Subjects will be summarized by treatment group.

The Safety Analysis Set (SAS) will include all subjects from Cohort 1 and Cohort 2 who were enrolled into VC02-101 or VC02-102 and in whom an implant surgery was attempted, regardless of whether any VC-02-300 units or sentinel-sized units were actually implanted. The SAS will be used for safety summaries. All subjects enrolled in Protocol VC02-102 are part of Cohort 1.

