#### 4.6.6.1 Daily and Weekly Exogenous Insulin Dose

Baseline average daily and average weekly exogenous insulin dose requirements will be calculated using up to 28 days of data. Baseline average daily and average weekly insulin requirements will be calculated using data starting at Day -3 (i.e., the day prior to immunosuppression induction) and working backwards for up to 28 days (through Day -30). For instances in which the available pre-implant dataset provides <28 days of data, the dataset will be supplemented with post-implant data, using data from Day 4 forward until 28 days of data is available. Data from days on which an MMTT or SOGCT was performed, will not be included in the calculation.

At Weeks 16, 26, 39, 52, 78, and 104, the last 7 daily total exogenous insulin doses recorded in the log will be used to calculate the average daily and the average weekly exogenous insulin dose at that visit. The last 7 daily records must be within the previous 14 calendar days and may not include a day in which an MMTT or SOGCT was performed. There must be at least 4 days worth of data for a particular timepoint to be considered evaluable. The weekly average value will be calculated as:

7 \* (sum of the insulin doses during the period / number of days with insulin doses in the period).

In each period, subjects must have four different days with recorded exogenous insulin doses in order for the value to be calculated.

The percent reduction in average weekly exogenous insulin dose from baseline at these visits will be calculated as:

(Average weekly insulin dose at post-baseline visit - baseline average weekly insulin dose)\*100/ baseline average weekly insulin dose.

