- ix. the number and percentage of subjects experiencing a TEAE by SOC, PT and related to immunosuppressive drug regimen.
- x. the number and percentage of subjects experiencing a TESAE by SOC and PT
- xi. the number and percentage of subjects experiencing a TESAE by SOC, PT and toxicity grade
- xii. the number and percentage of subjects experiencing a TESAE by SOC, PT and relationship to investigational product
- xiii. the number and percentage of subjects experiencing a TESAE by SOC, PT and relationship to the surgical procedures required for VC-02 administration
- xiv. the number and percentage of subjects experiencing a TESAE by SOC, PT and relationship to immunosuppressive drug regimen.
- xv. the number and percentage of subjects experiencing a TESAE by SOC, PT and related to investigational product
- xvi. the number and percentage of subjects experiencing a TESAE by SOC, PT and related to the surgical procedures required for VC-02 administration
- xvii. the number and percentage of subjects experiencing a TESAE by SOC, PT and related to immunosuppressive drug regimen.
- xviii. the number and percentage of subjects experiencing a TEAE leading to study withdrawal by SOC and PT

In the overall summary of TEAEs table (i), besides tabulating the number and percentage of subjects, the total number of TEAE episodes will also be provided. If a subject has repeated episodes of a particular TEAE, all episodes will be counted in the summary table's total number of episodes.

In the remaining summary tables, the incidence of TEAEs will be calculated by dividing the number of subjects who have experienced the event by the total number of subjects in the SAS. Thus, the incidence of TEAEs is shown in terms of the total number of subjects and not in terms of the total number of episodes. If a subject has repeated episodes of a particular TEAE, only one episode per toxicity grade, or one episode per causal relationship, will be counted in the summary tables.

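### AE incidence tables count only events from the implant date on, but the Cohort 1 primary endpoint covers immunosuppression-related AEs without that limit, and immunosuppression may start up to four weeks earlier

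*SAP*

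**What the plan says.** **Emergence rule.** SAP 7.2.1: "A treatment-emergent adverse event (TEAE) is defined as an AE that starts on or after the date of implant surgery". Protocol 8.5 gives the same definition.

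**Tables.** SAP 7.2.7 lists summaries i to xviii, all of TEAEs or treatment-emergent SAEs (TESAEs). Table ix, for example, gives "the number and percentage of subjects experiencing a TEAE by SOC, PT and related to immunosuppressive drug regimen". Protocol 10.4.3 agrees: "The summarization of AEs will focus on only those events that are TEAEs". It leaves all other reported AEs to the listings.

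**Endpoint.** Protocol 2.2.1 and SAP 2.2.1 include, in the Cohort 1 primary endpoint, the incidence of AEs causally related to VC-02, "the surgical procedures required for VC-02 administration, and the immunosuppressive drug regimen". Neither text limits this to TEAEs.

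**Timing of immunosuppression.** Protocol 5.2 permits basiliximab, MMF, tacrolimus combined with MMF, and sirolimus from Visit 2 (Week -4). Sirolimus, if used, has a trough target to be reached by Week -2.

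**AE collection.** Protocol 8.1.5: "All AEs with a start date occurring between Visit 2 (Week -4) and through the last subject visit must be recorded on the CRF".

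**Safety set.** SAP 4.2 restricts the Safety Analysis Set (SAS) to enrolled subjects "in whom an implant surgery was attempted".

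**The concern.** The plan treats immunosuppression as one of three formal causality components (Protocol 8.1.1, SAP 7.2.3) and puts its AEs into a primary safety endpoint. The clock for counting those AEs starts with a different component, the surgery. The two starting points can differ by weeks.

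At stake is whether the tables deliver the endpoint as worded. An AE that the investigator attributes to MMF or sirolimus before surgery belongs to the endpoint, yet no planned table counts it. The omission falls in the period when these drugs are first given, and in the immunosuppression tables it can only lower the count.

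**Working it through.** No figure in the plan needs reproducing; the point turns on definitions.

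**1. Event population of the tables.** Tables i to ix and xviii are TEAE tables (10) and x to xvii are TESAE tables (8); 10 + 8 = 18. Table i also contains TESAE lines. None covers AEs that start before the implant date. SAP 7.2.7 opens by bringing in all post-consent AEs, but that sentence concerns MedDRA coding. The implant tolerability summary in SAP 7.6.3 takes AEs related to product or surgery, so it does not fill the gap.

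**2. Earliest exposure (Protocol 5.2).**

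| Agent | Cohort | Recommended timing | Earliest permitted |
|---|---|---|---|
| Basiliximab | 1 (2 if continued) | Day 1 and Day 5 | Visit 2 |
| MMF | 1 and 2 | no fixed day | Visit 2 |
| Tacrolimus with MMF | 1 and 2 | no fixed day | Visit 2 |
| Sirolimus | 1 and 2, if used | trough target by Week -2 | Visit 2 |
| ATG | 2 only, conditional | Days -2, -1 and 1 required | Visit 2 |

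**3. Lead time.** Week -4 is 4 × 7 = 28 days before implant, and Protocol 6.2 requires at least two weeks (14 days) between Visits 2 and 3. A start at Visit 2 therefore gives roughly 14 to 28 days of exposure before the TEAE window opens. A later start gives less.

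**4. One event followed through.** Suppose a Cohort 1 subject starts MMF at Visit 2 and has an AE on Day -10, judged definitely related to immunosuppression.
- Protocol 8.1.5: recorded.
- Protocol 2.2.1: part of the primary endpoint.
- SAP 7.2.1: not treatment-emergent.
- SAP 7.2.7: in no table, only in the listing.

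The tables count subjects. If the same kind of event starts again on or after the implant date with the same relationship, the subject still appears in that row of table ix. Otherwise the subject is missing from it.

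**5. Size.** The documents give no pre-implant AE rate, so the undercount cannot be estimated. For illustration only, assume that a proportion p of subjects, 5% to 30%, have an immunosuppression-related AE before implant. Then the expected number is n × p, and P(at least one) = 1 − (1 − p)^n.
- n = 15: 15 × 0.05 = 0.75 to 15 × 0.30 = 4.5 subjects; P = 0.54 to 0.995.
- n = 3: 0.15 to 0.9 subjects; P = 0.14 to 0.66.

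These are upper limits on the subjects missing from a row, because of the repeat-event condition in step 4.

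As a share of immunosuppression time, a lead of 2 to 4 weeks is 2/(2 + 104) = 1.9% to 4/(4 + 104) = 3.7% if units stay to Week 104. It is 2/18 = 11% to 4/20 = 20% if follow-up ends at Week 16.

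**6. Cohort 2, general safety tables only.** If the conditional ATG course is used on its recommended days, the required doses are 0.5 + 1.0 + 1.5 = 3.0 mg/kg. Of these, 0.5 + 1.0 = 1.5 mg/kg (50%) falls before Day 1.

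**7. Subjects never taken to surgery.** Protocol 5.1.4 places enrollment at Visit 3 (Day 1), and the SAS needs an attempted implant. A subject who takes immunosuppression from Visit 2 and stops before surgery is outside the SAS, and so outside tables i to xviii.

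**The case against.** **The choice is deliberate and consistent.** Both documents anchor emergence to the investigational product, and Protocol 5.2 calls the immunosuppressants adjunct treatment. This stands as an explanation, but it does not reconcile the tables with an endpoint that names the immunosuppressive regimen and says AEs.

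**The events are not hidden.** They are recorded from Visit 2 and listed with grade, relationship and a TEAE flag. SAEs are reportable from consent, and the DSMB reviews cumulative Cohort 1 data. With 3 to 15 VC02-101 subjects in Cohort 1, a count could be made by hand from the listing. This lowers the severity, but a listing is still not an incidence.

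**A reader might infer that half of induction precedes the window for the primary safety endpoint.** The documents do not support that. ATG stands only under Cohort 2 induction, and only if cell viability proves insufficient; the primary endpoint of Cohort 2 is C-peptide AUC. Cohort 1 induction is basiliximab, recommended on Days 1 and 5, both inside the window. Likewise, the SAP places induction just after Day -3 in its baseline derivations (4.6.3, 4.6.4, 4.6.6.1, 4.6.7). Those are efficacy derivations, and SAP 4.2 excludes Cohort 1 from the efficacy set, so they say nothing about Cohort 1.

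**Early dosing is mostly permitted, not required.** This is correct. Only sirolimus, with its Week -2 target, implies pre-implant dosing in Cohort 1, and only if it is used.

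**The net direction is not certain.** SAP 7.2.3 places unlikely-related events in the combined related category, which pushes tables vii to ix and xv to xvii upward. Some partial dates in the implant month default to treatment-emergent (SAP 4.4), and any AE dated Day 1 counts even if it precedes surgery. These effects may offset part of the loss, but they do not restore the omitted events.

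**Unimplanted subjects would show as screen failures with reasons (SAP 5.1).** They may well, but that is disposition and gives no AE incidence. To say that a regimen whose toxicity prevents implantation would look safer is conjecture; the documents do not show that it would happen.

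**Conclusion.** The concern holds as a mismatch between endpoint and tables. For Cohort 1, the tabulated incidence of immunosuppression-related AEs can understate the primary endpoint as written, because AEs starting before the implant date reach only the listings. The size is unknown: it depends on how many subjects start early, how many then have a related AE, and how many of those have no matching event afterwards. In Cohort 2 the same gap touches the general safety tables. Subjects dosed but without an attempted implant appear in no AE table.

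The conclusion assumes that the endpoint wording is meant literally. The dosing text of VC02-102, whose subjects the SAP pools into Cohort 1, is not in the documents, so nothing is claimed about them. No hypothesis is tested on this endpoint and the data are kept, so this is a point that should be fixed, not one that invalidates the plan.

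**What to change.** In SAP 7.2.1 and 7.2.7, for the summaries by relationship to immunosuppression (tables i.e, i.k, vi, ix, xiv and xvii), count AEs that start on or after the earlier of the first study immunosuppressant dose and the implant date. Keep the implant date for the VC-02 and surgery tables. Add a short summary of AEs and SAEs in subjects who received study immunosuppression but had no attempted implant.

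The cost is SAP wording, one derived date and slightly more programming. AE onset dates are collected from Visit 2, and SAP 5.5 already lists medication start dates. The one consequence to accept is that the reported immunosuppression-related incidence can only stay the same or rise. The change is to counting only; no dosing change is implied.
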